This study will investigate neuropsychological disease and treatments before and after severe COVID-19 disease. The two main aims are:

1. to evaluate the associations of pre-existing neuropsychological diseases and treatments with severe COVID-19 outcomes in comparison to patients without pre-existing neuropsychological pathology;

2. to evaluate the associations between hospital or ICU admission due to COVID-19 and neuropsychological sequelae following discharge home in comparison to patients with ICU admission due to non-COVID-19 severe acute respiratory infections (SARI).

Objectives

- 1. To assess whether pre-existing neuropsychological diseases (by separate diseases and overall) are associated with severe COVID-19 outcomes (hospital and ICU admission and death) in comparison to the general population.
- 2. To assess whether pre-existing neuropsychological treatments (as a class and individually where possible) are associated with severe COVID-19 outcomes (hospital and ICU admission and death) and whether these explain disease associations in comparison to those not receiving such treatments.
- 3. To assess whether the risk of severe COVID-19 outcomes with prior neuropsychological disease differs from the risk of severe outcomes with SARI.

After discharge following a hospital admission for COVID -19 infection:

- 4. To assess the incidence of new neuropsychological diseases up to one year after hospital and ICU discharge following treatment for COVID-19 disease.
- 5. To compare the incidence of new neuropsychological diseases up to one year after hospital and ICU discharge with COVID-19 disease to the incidence following discharge after treatment for SARI.

Summary of the potential impact

This study will provide a better understanding of how pre-existing psychopathology and concomitant medication affect the risk of hospital and ICU admission and death due to COVID-19 and how any differences between those with and without preexisting psychopathology and COVID-19 infection compare to other severe acute respiratory infections. We will discover the neuropsychological sequelae of admission to a hospital or ICU with COVID -19 disease, taking into account prior neuropsychological disease and whether these differ from patients discharged from an ICU following SARI. These findings will be key to prevention and management of ongoing problems for these patients.

METHODS

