For cohort two, our primary outcome is the first occurrence of either hospital admission with SARI in the HES dataset (defined as a new ICD-10 code J09-J22 in the HES dataset) or ICU admission in the ICNARC CMP dataset with SARI (defined as any admission with unique diagnostic code any one of RE129 RE131 RE82 RE50 RE86 RE94 RE75 RE133 RE132 RE121 RE1 RE128 RE16 RE130 RE117 RE42 RE41) or death. Secondary outcomes will be each of these three events considered separately (I.e. SARI related hospital admission, ICU admission, death).

Aim 2.

Our primary outcome is development of new neuropsychological disease up to 1 year following hospital discharge which we define as having received a diagnostic code as below:

- Anxiety and stress-related disorders [ICD F40-48 and corresponding Read codes]
- Mood disorders [ICD F30-39 and corresponding Read codes]
- Psychotic disorders [ICD F20-29 and corresponding Read codes]
- Dementia [ICD F00-F03, G30, G31.0 ? and corresponding Read codes]

Secondary outcomes are the diagnosis of new neuropsychological disorders (as defined above) with treatment, and where numbers are available the new diagnosis with or without treatment of each class of disorders, each considered as a separate endpoint.

Neuropsychological treatments are defined as:

- Hypnotics and anxiolytics: (hypnotics, anxiolytics, barbiturates and methyprylone, benzodiazepines)
- Antidepressant drugs (Tricyclic and related antidepressant drugs, Monoamine-oxidase inhibitors, Selective serotonin re-uptake inhibitors, Other antidepressant drugs)
- Drugs used in psychoses and related disorders (Antipsychotic drugs and depot injections, Lithium salts, Phenothiazine derivatives)

Definition of exposures

Aim 1

Neuropsychological disease will be defined as an ordinal variable with the following three categories: no relevant diagnosis or drugs; diagnosis ever recorded without recent drug treatment; diagnosis present with recent drug treatment (with at least two prescriptions for neuropsychological treatments as above within the six months preceding study entry).

Our primary exposure is active neuropsychological disease on the study entry date which we define as having received a diagnostic code as above (24th January 2020 for cohort 1 and 24th January 2015 for cohort 2).

Aim 2.

The primary exposure is a hospital or ICU admission resulting from COVID-19 infection. Comparator exposures are hospital or ICU admission resulting from SARI.

Covariates

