- oral steroids

Intensive care stay (Aim 2)

- Length of stay
- Duration of advanced respiratory support (invasive ventilation)
- Use of sedation in the first 24 hours of admission

Effect Modifiers

For aim 1, we assessed these potential confounders by creating directed acyclic graphs (DAG) to determine which variables were likely to be to some extent caused by the presence of prior neuropsychological disorders (as the exposure of interest), and which were not likely to be caused by the presence of prior neuropsychological disorders, but were thought to be independently potential predictors of severe Covid outcomes.

Variables from the above list to be included in the model are all those grouped under: demographics; co-morbidities; lifestyle factors; plus prescription of any immunosuppressants and/or anticoagulants. Other medications (as these are not believed to affect the risk of severe Covid outcomes), and in-hospital factors (length of stay and use of sedation during intensive care admission, as these are outcomes potentially caused by Covid severity) will not be adjusted for.

For aim 2, our exposure of interest is admission to intensive care with SARI (compared to admission to intensive care with SARI. This exposure occurs at a fixed time which is used as the baseline for our time to event analysis in predicting the outcome of interest, and all other variables listed above are measured before this baseline. Therefore (depending on the available sample size and number of events), all the previously listed covariates of interest may be included in our adjusted models.

Data sources

Intensive Care Unit admission data will come from the ICNARC CMP dataset Hospital admission and mortality will come from the HES dataset

All exposures and confounders and neuropsychological outcomes will come from the QResearch database.

COVID-19 infection test status will come from the national registry of COVID-19 RT-PCR positive test results from Public Health England (PHE).

Bias

To limit the possible impact of COVID-19 testing bias (collider bias) we will analyse the entire QResearch eligible population, rather than restricting analysis to only those with a positive COVID-19 test.

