Royston Parmar flexible parametric survival models will be used to estimate the hazard ratio of severe COVID-19 outcome (hospital or critical care admission and death) in cohort 1 for patients with neuropsychological disease at study entry compared with those without disease, and for individual neuropsychological diseases and treatments.

This analysis will be adjusted for the listed covariates. The age variable will be included as a restricted cubic spline rather than a linear term. Before commencing analysis, we will assess the numbers of patients with each comorbidity, and may if necessary group the presence of certain less common comorbidities together. Any such grouping will be done on the basis of clinical similarities only and prior to examining any outcomes by comorbidity. We may also include a time-varying binary covariate to record any new diagnosis and/or treatment which occurs after study entry in patients originally free from both diagnosis and treatment, depending on the number of these events. Proportional hazards assumptions will be tested, and time dependent terms will be included if the hazard ratio changes over time (I.e. if the association between neuropsychological disease and risk of severe COVID-19 has changed during the course of the pandemic). A random frailty term will be included to account for similarities amongst patients registered in the same primary care practice. Possible interactions between exposure and age, sex and ethnicity will be considered and tested using a Wald test.

The same methods will be used for secondary analyses in which the main exposure variable will be defined as either the presence of a specific class of neuropsychological disorder or any other neuropsychological disorders or no disorder.

The primary analysis will be used to estimate the hazard ratio of severe SARI outcomes in cohort 2 using the same exposure variables.

If non-proportional hazards are observed in either cohorts 1 or 2, then maximum follow-up time will be capped at 1 year and a time-dependent covariate will be added to the analysis of both cohorts to maintain the comparability of results.

Aim 2.

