This study will present analysis of the association between psychopathology and its treatments and the risks of severe COVID-19 disease. We will also report the risks of developing psychopathological outcomes following ICU admission with COVID-19 disease in comparison to admission with other severe respiratory disease.

An advantage of this work in comparison to previous database analyses is the detailed information available on therapies within the QResearch database. This will allow us to investigate whether previously reported associations between COVID-19 infection and neuropsychological conditions are related to specific treatments rather than the diagnoses alone [3, 8].

As far as we are aware analysis of the post-ICU neuropsychological consequences of COVID-19 disease has not been undertaken. We are not aware of previous work linking the primary care and ICU record. As a result, previous work on neuropsychological outcomes following ICU has been severely limited both by a lack of knowledge of whether patients had neuropsychological disease prior to their ICU admission [9, 16] and by limited understanding of the treatments applied following discharge in the community [9]. Our work will provide understanding of this pathway both for patients with COVID-19 disease and for the comparator group of patients admitted to an ICU with SARI.

References

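### The adjustment set stated for Aim 1 was derived for the disorder as exposure; applied as written to drug-class hazard ratios, it leaves measured confounding by indication and gives Objective 2 no stated joint model of diagnosis and drug class.

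*Protocol*

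**What the plan says.** Objective 2 covers pre-existing treatments, as a class and individually where possible, and asks "whether these explain disease associations in comparison to those not receiving such treatments". The Hypothesis section likewise ties the excess risk to particular medication classes.

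Statistical Methods, Aim 1, sets out a Royston-Parmar model for severe COVID-19 in cohort 1, to give hazard ratios "for patients with neuropsychological disease at study entry compared with those without disease, and for individual neuropsychological diseases and treatments". It adds: "This analysis will be adjusted for the listed covariates". The secondary analyses recode the main exposure as "either the presence of a specific class of neuropsychological disorder or any other neuropsychological disorders or no disorder". Cohort 2 uses the same exposure variables for SARI.

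The Effect Modifiers section fixes the Aim 1 set: "Variables from the above list to be included in the model are all those grouped under: demographics; co-morbidities; lifestyle factors", plus immunosuppressants and anticoagulants. It says that the directed acyclic graph behind this choice took prior neuropsychological disorder as the exposure.

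Definition of exposures, Aim 1, gives three levels: neither diagnosis nor drugs; a diagnosis without recent treatment; and a diagnosis with recent treatment, "with at least two prescriptions for neuropsychological treatments as above within the six months preceding study entry".

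**The concern.** A drug class is prescribed because of a diagnosis, and the diagnosis may itself raise the risk of severe COVID-19. When recipients are compared with everyone not receiving the drug, the diagnosis is the leading confounder, followed by co-prescribed classes. An antipsychotic hazard ratio could then carry the effect of dementia or psychosis, and an antidepressant hazard ratio that of mood disorder or of sedatives taken alongside.

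What is at stake is the question that the Discussion presents as an advantage of this database: whether reported associations "are related to specific treatments rather than the diagnoses alone". To separate the two, diagnosis and drug class must appear in the same model, or drug users must be compared with non-users within a diagnosis. The Introduction itself warns that earlier drug-class findings may be subject to residual confounding.

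**Working it through.** **Step 1. What the stated set contains.** The Covariates section was checked item by item.

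- Co-morbidities: epilepsy, Parkinson's disease, Huntington's disease, traumatic brain injury and learning disability are listed. Anxiety, mood disorder, psychotic disorder and dementia are not.
- Medications: no hypnotic or anxiolytic, antidepressant or antipsychotic is listed. Of the medications that are listed, only immunosuppressants and anticoagulants enter the Aim 1 model.
- Exposure coding: the secondary coding is by disorder class. No drug-class coding is given, and no model is stated that holds diagnosis and drug class together.

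**Step 2. What the three-level exposure can show.** Level 3 against level 2 compares treated with untreated people who all have a diagnosis, so it bears on treatment of any kind. The protocol does not name this contrast. It pools four diagnoses and three drug classes, and it has no level for people prescribed these drugs without a coded diagnosis.

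**Step 3. Illustration of size.** The protocol gives no figure to reproduce, so every input here is an assumption. For a drug with no effect and a rare outcome,

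apparent HR = [1 + p1(h − 1)] / [1 + p0(h − 1)],

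where h is the hazard ratio of the omitted condition and p1 and p0 are its prevalences in users and non-users. For antipsychotics with dementia omitted:

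| h | p1 | p0 | Calculation | Apparent HR |
|---|---|---|---|---|
| 2 | 0.10 | 0.01 | 1.10 / 1.01 | 1.09 |
| 3 | 0.20 | 0.01 | 1.40 / 1.02 | 1.37 |
| 3 | 0.30 | 0.01 | 1.60 / 1.02 | 1.57 |

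Other assumptions give other ranges:

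- Diagnosis in 70–100% of users and 10–20% of non-users, h from 1.3 to 3: from 1.21/1.06 = 1.14 to 3.0/1.2 = 2.50.
- Another psychotropic class omitted, co-use 30–50% in users and 5–10% in non-users, h from 1.3 to 2: from 1.09/1.03 = 1.06 to 1.5/1.05 = 1.43.

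**Step 4. Check by simulation.** One million people; diagnosis prevalence 20%; drug use 40% with and 2% without the diagnosis; diagnosis HR 2; drug HR 1. All are assumed.

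| Contrast | Estimate |
|---|---|
| Users vs non-users, diagnosis not in the model | 1.60 |
| Users vs non-users, diagnosis in the model | 1.00 (95% CI 0.95 to 1.05) |
| Level 3 vs level 1 | 1.97 |
| Level 2 vs level 1 | 1.96 |
| Level 3 vs level 2 | 1.00 |

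Of the level contrasts, only level 3 against level 2 isolates treatment.

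**The case against.** The strongest reply is that silence is not exclusion. The diagnoses and drug groups are defined as exposures, and exposures do not normally appear in a confounder list. The protocol does not say whether individual diseases and treatments enter singly or jointly, the graph for Aim 1 is not visible, and an unseen SAP could specify a joint model. This stands to the extent that a reader might infer that the protocol rules out joint entry; the documents do not support that. But the protocol is not merely silent. It states an adjustment set with a rationale built for a different exposure, and an SAP that followed it literally would reproduce the problem.

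A reader might also infer that no planned analysis bears on treatment. That goes too far: level 3 against level 2 does, for any treatment. Nor does the Discussion assert a finding about drugs; it poses a question.

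The illustrative figures are crude. The model already includes age as a spline, care-home residence, stroke and Parkinson's disease. The relevant inputs are conditional on these, and the bias may well be smaller.

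The planned E-value does not settle the matter. It addresses unmeasured confounding, whereas diagnosis and prescriptions are recorded in QResearch.

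**Conclusion.** The point holds for drug-class and individual-drug hazard ratios against non-recipients. The stated adjustment set is unsuited to that exposure, and the part of Objective 2 about explaining disease associations has no stated analysis at drug-class level. For treatment of any kind, the three-level exposure is a partial safeguard that the protocol does not yet use explicitly.

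The size of the bias cannot be given from the documents. The range 1.09 to 1.57 rests on assumed dementia prevalences and hazard ratios and takes no account of the stated covariates. With about 8.3 million adults, a bias of this order could still come with a narrow interval, although precision depends on event numbers among users, which are not given.

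Two stronger conclusions are not supported: that the drug results will necessarily be wrong, and that the primary disease analysis is affected. Leaving drugs out of the primary analysis is legitimate, since treatment may lie on the pathway from disease to outcome.

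**What to change.** - **Definition of exposures, Aim 1:** define one indicator for each of the three drug classes, using the existing rule of two or more prescriptions in the six months before entry, regardless of whether a diagnosis is coded.
- **Statistical Methods, Aim 1:** add a secondary model, in cohorts 1 and 2, that enters the four diagnosis indicators and the three drug-class indicators together with the stated covariates.
- **Reporting:** give drug-class hazard ratios conditional on diagnosis, disease hazard ratios with and without the drug terms, and the named contrast of level 3 against level 2.
- **Primary analysis:** leave the disease analysis unadjusted for drugs.
- **Limits to state:** confounding by severity may remain after adjustment for diagnosis, and the comparison with and without drug terms is descriptive, not proof of mediation.

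The cost is protocol wording and one more model on variables that the study already needs. Intervals will be somewhat wider for drug classes closely tied to one diagnosis; by how much depends on event numbers that the protocol does not give.

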The following variables of interest were chosen as either due to known association with risk of developing severe COVID-19 and/or known associations with neuropsychological disease. Distributions of each variable will be summarised by cohort using descriptive statistics.

Demographics (Aims 1 & 2)

- Age
- Gender
- Material deprivation by quintile of Townsend deprivation score

- Ethnicity (White, Indian, Pakistani, Bangladeshi, other Asian, Black African, Chinese, and other ethnic group),
- Geographical region
- Domicile (homeless, care home residence, neither)
- Household size

Lifestyle (Aims 1 & 2)

- Body mass index (BMI)
- Smoking status (non-smoker, ex-smoker, light smoker: 1–9 cigarettes/day, moderate smoker: 10–19 cigarettes/day, heavy smoker: ≥20 cigarettes/day, not recorded)
- Alcohol intake (none, trivial: <1 unit/day, light: 1–2 units/day, medium: 3–6 units/day, heavy: 7–9 units/day, very heavy: >9 units/day, not recorded).

Co-morbidities (Aims 1 & 2)

- Cardiovascular diseases coronary heart disease, stroke/transient ischaemic attack, atrial fibrillation, congestive cardiac failure, thromboembolism, peripheral vascular disease, congenital heart disease, hypertension
- Respiratory diseases asthma, chronic obstructive pulmonary disease, rare lung conditions (bronchiectasis, cystic fibrosis, alveolitis), pulmonary hypertension or pulmonary fibrosis
- Endocrine diseases type 1 and 2 diabetes, hypothyroidism
- Chronic kidney disease
- Neurological conditions- epilepsy/seizures, Parkinson's disease, motor neurone disease, multiple sclerosis, myasthenia gravis, Huntington's disease
- Cancer blood cancer, respiratory tract cancer, and other relevant cancer
- Bone and joint conditions- osteoarthritis, rheumatoid arthritis or Systemic Lupus Erythematosis (SLE), osteoporosis, osteoporotic fracture (hip, spine wrist, humerus)
- Gastrointestinal diseases liver disease, liver cirrhosis
- Transplants solid organ transplant (excluding kidney and bone marrow), bone marrow or stem cell transplant
- Sickle cell disease or severe immunodeficiency
- Traumatic brain injury
- Learning disability/Down's syndrome, cerebral palsy

Medications/treatments (Aims 1 & 2)

- antihypertensive drugs,
- aspirin,
- statins,
- Anticoagulants,
- non-steroidal anti-inflammatory drugs,
- bisphosphonates,
- oral contraceptives,
- hormone replacement therapy,

- anticonvulsants
- chemotherapy
- radiotherapy
- immunosuppressant medication
- leukotriene or long-acting beta-agonist

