For aim 1, the various different neuropsychological conditions of patients in cohort 1 are likely to result in varying levels of exposure to covid-19, compared to the populations without these conditions, with some conditions likely to have a protective effect, but in other conditions the reverse is expected. We have added a secondary analysis to examine the effect of specific conditions in order to evaluate this.

For aim 2, the two cohorts have experienced their exposure of interest (ICU admission with either COVID or SARI) during different time frames. Patients with SARI (admitted to ICU between 2015 to 2020) will have longer follow-up, but patients with COVID (admitted to ICU during 2020/21) may have benefited from the recently increasing public awareness of mental health conditions. To combat this, we have capped all follow-up at a maximum of 1 year post ICU discharge, and we will include a time-dependent covariate to assess whether risk varies with time post discharge. We have also included a cohort of patients with SARI admitted during 2020/21 for comparison with the COVID cohort during the same time frame.

We will derive the E-value to estimate the extent unmeasured confounding.

Study Size

For aim 1 we will use the entire QResearch database of approx. 8.3 million adult patients to maximise precision and minimise selection bias. We chose to use the last 5 years of ICNARC data for SARI comparisons to use recent data whilst having sufficient numbers for comparison taking into account the numbers from previous studies and after linkage [13, 14].

For aim 2, we will use all known ICU admissions from the ICNARC database for SARI and/or COVID who can be linked to the QResearch database. In cohort 3 the expected sample size is in the region of 11,000 admissions in total, for cohort 4 it is likely to be in the region of 7,000 admissions per year, and for cohort 5 around 3,500 patients.

Quantitative variables

Quantitative variables will be treated as continuous variables without categorisation. Descriptive summary statistics (mean and standard deviation, median interquartile range or number (%) as appropriate) will be used to present sociodemographic and clinical characteristics of patients with and without COVID-19 infection for those with and without neuropsychiatric conditions or treatments.

Statistical Methods

Aim 1.

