Cause-specific Royston Parmar flexible parametric models will be used to estimate the hazard ratios of developing new neuropsychological diseases after having received intensive care, comparing patients who received intensive care for COVID-19 (cohort 3) vs those who received intensive care for SARI (cohort 4). This model will adjust for all previously listed covariates. The age variable will be included as a restricted cubic spline rather than a linear term. Follow-up will start on the date of discharge from hospital.

Proportional hazards assumption will be tested, and time dependent terms will be included if the hazard ratio changes over time. A random frailty term will be included to account for similarities amongst patients admitted in the same critical care unit

A limited number of two-way interactions which are considered to be clinically or biologically plausible will be identified prior to analysis, and tested using a Wald test.

Primary care data on some potential confounding variables is incomplete (e.g. smoking status, alcohol intake, ethnic group, BMI). Reason for admission is mandatory for all records in the ICNARC database (the core dataset for aim 2), so classification of these reasons as either SARI or COVID related will be non-missing for all patients. Only admission records for completed critical care stay (non-missing length of stay and survival status at end of critical care) will be included (n.b. outcomes are missing in <1% of COVID ICU admissions to date). Remaining variables from the critical care stay are use of sedation in the first 24 hours, and duration of advanced respiratory support, which are missing for a small number of patients (<1.5%).

Both aims.

To allow data analysis with all eligible patients, we will impute missing data in all cohorts. We will use multiple imputation with chained equations under the missing at random assumption to replace missing values and use these values in our main analyses [15]. We will include all exposure and confounding variables in the imputation model, along with the Nelson–Aalen estimator of the baseline cumulative hazard, and the outcome indicator. We will carry out five imputations. Analysis models will be fitted in each imputed dataset and Rubin's rules to will be used to combine the results across the imputed datasets.

As the analyses are on time to event data, patients will be censored at the date when they are lost to follow-up as defined in cohort definitions above.

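### Only age is given a non-linear form; BMI, naturally read as linear, could leave residual confounding as large as the confidence interval in Aim 1

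*Protocol*

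**What the plan says.** Under Quantitative variables, the protocol sets a general rule: "Quantitative variables will be treated as continuous variables without categorisation". Under Statistical Methods, Aim 1, it makes one exception: "The age variable will be included as a restricted cubic spline rather than a linear term". The Aim 2 text repeats that sentence. No other covariate is given a non-linear form.

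BMI is listed under Lifestyle for both aims, without categories. The section on effect modifiers puts all lifestyle factors into the Aim 1 model. Several other covariates are listed in bands and so are not straight-line terms: "Material deprivation by quintile of Townsend deprivation score", smoking status and alcohol intake. The remaining uncategorised quantitative covariates are few: "Household size" in both aims, and, for Aim 2, length of stay and duration of invasive ventilation.

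The Study Size section states: "For aim 1 we will use the entire QResearch database of approx. 8.3 million adult patients". The Both aims text plans multiple imputation, and BMI is among the variables named as incomplete.

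**The concern.** By contrasting the spline for age with a linear term, the text suggests that a linear term is the default elsewhere. An analyst who followed it literally would fit BMI as one slope.

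If both low and high BMI go with worse outcomes, one slope cannot fully adjust for BMI. What is left over biases the exposure hazard ratio when BMI is distributed differently in patients with and without neuropsychological disease. The exposure pools anxiety, mood disorders, psychotic disorders and dementia. A wider BMI spread in so mixed a group is plausible, but the protocol gives no data on it.

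In a cohort of millions, the confidence interval may be too narrow to cover such an error. The same models serve cohorts 1 and 2, so the COVID-19 versus SARI comparison could also be affected if the curvature differs between the two outcomes.

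The planned safeguards do not address this. The E-value concerns unmeasured confounding, and the complete-case analysis would repeat the same covariate form.

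**Working it through.** The protocol states no event rate, exposed share, BMI distribution, BMI-risk curve or expected interval width, so there is no figure of its own to reproduce. Two quantities were computed and compared.

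**Step 1. Precision.** The 95% half-width on the log hazard ratio is 1.96/√(D·p·(1−p)), where D is the number of events and p the exposed share. From the protocol: N = 8.3 million for Aim 1. Assumed: events in 0.2% to 2% of patients, and p from 1% to 25%.

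- 1% events gives D = 83,000. With p = 25%: 1.96/√(83,000 × 0.25 × 0.75) = 1.96/124.7 = 0.016.
- 1% events with p = 10%, 5% and 1%: 0.023, 0.031 and 0.068.
- Extremes: 0.011 (2% events, p = 25%) and 0.153 (0.2% events, p = 1%).

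**Step 2. Bias from a linear BMI term.** The true exposure effect was set to zero. True log risk was b × (BMI − nadir)², capped at 1.5. A Poisson rare-event model with exposure and linear BMI was fitted in the large-sample limit. All inputs are assumed:

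- BMI follows a shifted gamma distribution; in the unexposed, mean 27 and SD 5.
- b is 0.001, 0.002 or 0.004, so the hazard ratio 10 units from the nadir is exp(100b) = 1.11, 1.22 or 1.49.
- The nadir is 23 or 26, and p is 5% or 25%.

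| BMI in exposed (mean, SD) | Bias in log HR over the grid |
|---|---|
| 27, 5 (same as unexposed) | 0 |
| 27.5, 5.2 | 0.0002 to 0.002 |
| 28, 5.5 | 0.002 to 0.011 |
| 28, 6 | 0.008 to 0.037 |
| 28.5, 6.5 | 0.013 to 0.058 |
| 28, 5 (mean shift only) | −0.016 to −0.003 |

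The extremes are exp(−0.0157) = 0.984 and exp(0.0584) = 1.060, that is −1.6% to +6%. A correctly specified curved BMI term gives zero bias by construction.

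**Step 3. Comparison, Aim 1.**

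- p = 25%, 1% events (half-width 0.016): with SD 6 against 5, b = 0.004 and nadir 26, the bias is 0.032, twice the half-width. With b = 0.002 it is 0.0175, just above. With b = 0.001 it is about 0.008, below. At SD 5.5 or less in the wider-spread rows, it stays below throughout. A mean shift alone reaches about the half-width only at the strongest curvature.
- p = 5%, 1% events (half-width 0.031): the bias exceeds the half-width only toward the strong end, for example 0.037 at SD 6, b = 0.004, nadir 26.
- p = 1%: the half-width is 0.068 at 1% events and wider with fewer. The largest bias in the grid, 0.058 (computed at p = 5%), lies inside it. Only at 2% events (half-width 0.048) would that extreme fall outside.

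**Step 4. A second, independent calculation.** This simulation had 3 million people, about 24,000 to 26,000 events, 16–17% exposed and a true HR of 1.00. BMI was curved in both exposure and hazard.

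- Linear BMI gave HRs of 1.024, 1.061 and 1.077. Quadratic BMI gave 1.002, 1.019 and 0.998.
- The shifts are ln(1.024/1.002) = 0.022, ln(1.061/1.019) = 0.040 and ln(1.077/0.998) = 0.076.
- The half-width was 1.96 × 0.016 = 0.031, which scales to 0.031 × √(3/8.3) = 0.019 at 8.3 million.
- Its hazard curvature, 0.10 to 0.15 per (5 kg/m²)², means exp(0.4) = 1.49 to exp(0.6) = 1.82 at 10 units. It therefore starts where the grid in Step 2 ends.

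**Step 5. Aim 2.** From the protocol, cohort 3 has about 11,000 admissions, cohort 4 about 7,000 × 5 = 35,000, and cohort 5 about 3,500. With an assumed 2% to 15% events, the half-width is 0.152 to 0.055 for cohort 3 versus 4, and 0.269 to 0.098 for 3 versus 5. Cohort 3 is 11,000/46,000 = 24% of the first comparison, so the p = 25% results apply. Their largest bias, 0.048, is below every half-width for that comparison. The bias for 3 versus 5 is not reported here, but its intervals are wider still.

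**The case against.** The strongest objection is that the protocol never says BMI is linear. A spline is also continuous and uncategorised, so the proposed fix already complies with the text. The form of each covariate is often left to the analysis plan, which is not at hand. This stands in part. A reader might infer that the protocol prescribes a linear BMI term, but that is inferred from the contrast with age and is not stated. If the analysis plan already gives BMI a curved form, the point is settled. It is still fair to raise, because the protocol itself chooses to fix functional form and stops at age.

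Second, the size of the bias rests wholly on assumed inputs. That also stands. The calculations adjust for BMI alone, whereas the planned model includes an age spline, diabetes, hypertension, cardiovascular disease and more, which may absorb part of any curvature.

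Third, Aim 2 has tens of thousands of patients, not millions, and the protocol itself expects few events there. Adjustment for the full covariate list is also made conditional on sample size and events in one section. The argument from precision therefore does not carry over to Aim 2.

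**Conclusion.** The point holds as a minor specification gap in Aim 1. Residual confounding from a straight-line BMI term could be comparable to or larger than the 95% interval. Over the assumed inputs it runs from about −1.6% to +6% on the hazard ratio, against a half-width of about 1.6% at 1% events and 25% exposed. This needs curvature of at least moderate size, BMI distributions that clearly differ (mainly in spread), and a common exposure or many events. With similar BMI distributions the bias is negligible, and with a rare exposure it mostly lies inside the interval.

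A reader might go further and conclude that the bias would exceed the interval, or that it affects both aims. The documents support neither. They contain no BMI distribution, risk curve or event count, and for cohort 3 versus 4 the modelled bias stayed below every half-width computed.

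**What to change.** Under Quantitative variables and Statistical Methods, Aim 1, state that BMI enters the models for cohorts 1 and 2 as a restricted cubic spline, as age does. Pre-specify the number and position of the knots; the protocol gives none for age either, so both can be set together. Use the same form in both cohorts, so that the COVID-19 and SARI hazard ratios are adjusted alike. Because BMI is partly imputed, use an imputation model compatible with the curved term.

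For Aim 2, use the same form for BMI. Do likewise for length of stay and ventilation duration if they are retained and event numbers allow. This is for consistency only.

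The cost is two or three extra parameters per model, which is trivial in Aim 1. In Aim 2 it should be weighed against the number of events.
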